## **8.2 Study Discontinuation**

Syntimmune Inc. has the right to terminate or to stop the study at any time. Reasons for study discontinuation may include, but are not limited to the following:

- The incidence or severity of AEs in this or other related studies indicates a potential health hazard to subjects
- Subject enrollment is unsatisfactory
- Drug supply issues
- Excessive subject self-withdrawal
- Significant protocol violations (e.g., violation of eligibility criteria, dosing errors, missing data for study endpoint analysis)

## **8.3 Replacements**

Enrolled subjects withdrawn for a reason other than an AE will be replaced if they have not been dosed or have only received one dose of study drug at the time of discontinuation, up to one subject per cohort. Subjects who do not receive all doses of study drug will continue to be followed through all scheduled study visits.

## **8.4 Stopping Rule**

### **8.4.1 Dose-Escalation Stopping Rule**

Dose escalation decisions will be made by a Dose Escalation Committee (DEC) and will be based on safety and pharmacodynamic evaluations including but not limited to, dose-limiting toxicities, AEs, SAEs, and total IgG levels.

Dose-limiting toxicity (DLT) will be defined generally as severe (Grade 3) AEs occurring in  $\geq 2$  subjects that are determined to be clinically significant and considered related to study drug.

If 2 or more subjects at any time in any cohort (8 total subjects per cohort) have Grade 3 AEs that are determined to be clinically significant and considered to be related to study drug, dosing will be halted within that cohort and dose-escalation to a higher dose will not occur. If the dose-escalation stopping rule is met during Cohort 1 (10 mg/kg) all safety data and all available pharmacodynamics will be reviewed and the cohort may resume (if applicable) or a new cohort may be added at a dose at least 50% lower than the 10 mg/kg dose. If the stopping rule is not met in Cohort 1, dose-escalation may proceed up to a maximum of 30 mg/kg. If the dose-escalation stopping rule is met for the first time during Cohort 2, all safety data and all available pharmacodynamics will be reviewed and the cohort may resume (if applicable) or a new cohort may be added at a dose a minimum of 30% lower than the Cohort 2 dose. If the stopping rule is not met in Cohort 2, dose-escalation may proceed up to a maximum of 45 mg/kg; however, this cohort may also receive a dose equal to or less than 30 mg/kg based on evaluation of all safety and pharmacodynamic data.

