### 4.3 Overview of Study Design

This will be a multicenter, open-label study to assess the safety, tolerability, activity, PK, PD, and immunogenicity of 5 once-weekly IV infusions of SYNT001 to subjects with chronic pemphigus (vulgaris or foliaceus).

Planned doses of SYNT001 to be studied are 10 mg/kg and up to 30 mg/kg. Two cohorts of 8 eligible subjects each will receive 5 once-weekly 60-minute infusions of SYNT001 10 mg/kg or up to 30 mg/kg. Based on review of safety, PD, and clinical outcomes of the first cohort, the dose for the second cohort may be adjusted, but with a maximum dose of 30 mg/kg. Based on review of safety, PD and clinical outcomes from these 2 cohorts, a third cohort of up to 8 subjects may be treated at another dose, with a maximum dose of 45 mg/kg, but may also be lower than 10 mg/kg or between 10 and 30 mg/kg, inclusive.

Cohort	No. of Subjects	Dose
1	8	SYNT001 10 mg/kg
2	8	SYNT001 30 mg/kg

Cohorts will be dosed sequentially beginning with Cohort 1. The first 2 subjects will be dosed at least 24 hours apart. A review of the 24-hour safety data for the first subject will be performed to ensure that there are no overt safety concerns before dosing the second subject. A review of the 7-day safety data for the first 2 subjects will be performed prior to dosing the remaining 6 subjects in the cohort. This evaluation will include a review of AE/SAE reports, vital sign assessments, physical examinations, ECGs and clinical laboratory testing. The seriousness, severity, and relatedness of AEs/SAEs will also be considered in the safety evaluation. Safety data will be reviewed on a continuous basis throughout the study. All data through Day 42

(2 weeks after the last subject's last dose in Cohort 1) will be reviewed before Cohort 2 is initiated. Cohort 2 and Cohort 3, if added, will be dosed per the same schedule.

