Safety evaluations will be conducted by a dose escalation committee (DEC). The DEC will consist of the Medical Monitor, an Independent Clinical Expert and a Syntimmune Medical Officer. To assist in the safety assessments, the DEC may request that Investigators, other experts, or members within their organizations review the data and participate in the discussions. Dosing and dose escalation will proceed if the DEC has determined that it would be safe and appropriate to do so. In addition, over the course of the study, the DEC will review any drug-related SAEs to determine if modifications to the study or other measures are necessary to ensure the safety of the subjects.

On days where study drug is administered, vital sign and pulse oximetry measurements will be collected immediately prior to the infusion; 15, 30, and 45 minutes after the start of the infusion; at completion of the infusion; and 30 minutes, 1 hour and 2 hours following completion of the infusion.

On Days 0 and 28, PK blood samples will be collected prior to infusion start and then over the subsequent 48 hours. Subjects will remain at the clinic through the 6-hour PK sample collection and will return to the clinic for the 24- and 48-hour collections. Additional samples will be collected on Days 5 and 33.

On Day 0 photographs will be taken of active lesions. Follow-up photographs will be taken of the same areas on Days 33, 56, 84, and 112. If a subject begins a steroid taper, additional photographs will be taken at the clinic visit during which the decision to begin the taper is made.

Subsequent visits will occur on Days 1, 2, 5, 7, 12, 14, 19, 21, 28, 29, 30, 33, 42 and 56 for safety assessments, study drug dosing, sample collections, and other study procedures.

Subjects also will return to the clinic on Days 84 and 112 for follow-up visits. Subjects whose total IgG is not within 30% of their Day 0 baseline value and not above 500 mg/dL at the Day 112 visit will be referred for further management.

See [Table 1](#) for a schedule of all study events. To assess safety and tolerability, subjects will undergo physical examinations (PEs; including weight), vital sign measurements, clinical (safety) laboratory tests, AE assessments, concomitant medication assessments, and electrocardiograms (ECG).

**Note:** No vaccinations may be given from within 2 weeks of screening through Day 56. Following Day 56, subjects may receive vaccinations at the discretion of the Investigator.

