#### **8.4.2 Study Stopping Rule**

If any subject experiences a life-threatening AE (Grade 4) that is considered to be related to study drug, further dosing in all enrolled subjects will be suspended until the DEC has evaluated the event and determined the appropriate course of action. At any time during the study, the study may be discontinued if the DEC determines that further drug exposure would pose an undue risk to subjects.

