#### **8.4.3 Individual Stopping Rule**

Dosing for any individual subject will be discontinued (i.e., no further study drug will be given to that subject) if the subject experiences any study drug-related SAE or any study drug-related non-SAE adverse event that, in the judgement of the Investigator (following consultation with the Medical Monitor, if desired) suggest that it could be unsafe to administer further study drug to that subject. Additionally, a subject will be discontinued from further treatment with study drug, at the discretion of the Investigator with consultation with the Medical Monitor, if they require a significant increase in dose(s) of anti-pemphigus medication(s) for the management of pemphigus.

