### 9.2 Cohort Dosing

Cohorts will be dosed sequentially beginning with Cohort 1. The first 2 subjects will be dosed at least 24 hours apart. A review of the 24-hour safety data for the first subject will be performed to ensure that there are no overt safety concerns before dosing the second subject. A review of the 7-day safety data for the first 2 subjects will be performed prior to dosing the remaining 6 subjects in the cohort. Cohort 2, and Cohort 3 if added, will be dosed per the same schedule

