### 9.3 Timing of Dosing

On Days 0, 7, 14, 21, and 28, subjects will receive a 60-minute IV infusion of SYNT001 in the morning. The date and time the dose is administered will be recorded.

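### A Grade 3 stopping rule met late by a lower-dose cohort sets no interim pause for a higher-dose cohort already being dosed

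*Protocol*

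**What the plan says.** Section 8.4.1, repeated in the synopsis under the dose-escalation rules, is met when at least two of a cohort's eight subjects have Grade 3 adverse events judged clinically significant and drug-related. It sets no time limit. Two actions are fixed: "dosing will be halted within that cohort and dose-escalation to a higher dose will not occur". A review of all safety data and available pharmacodynamic data follows. For a Cohort 1 trigger the listed outcomes are that the cohort resumes, if that still applies, or that "a new cohort may be added at a dose at least 50% lower than the 10 mg/kg dose". For a first trigger in Cohort 2 the wording is parallel, with a reduction of at least 30%. Neither contingency mentions subjects already being dosed at a higher level.

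The timing comes from other sections:

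- **Dosing (9.3):** "On Days 0, 7, 14, 21, and 28, subjects will receive a 60-minute IV infusion of SYNT001 in the morning".
- **Opening of the next cohort (4.3, 11.5):** data through Day 42 "will be reviewed before Cohort 2 is initiated".
- **Adverse event collection (11.2, 7.18):** from consent to the last study visit, which is Day 112.

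Two other rules stop dosing. Section 8.4.2 covers a related Grade 4 event, after which "further dosing in all enrolled subjects will be suspended until the DEC has evaluated the event and determined the appropriate course of action". Section 8.4.3 stops an individual "if the subject experiences any study drug-related SAE or any study drug-related non-SAE adverse event that, in the judgement of the Investigator" makes further dosing look unsafe, or on a significant increase in that subject's anti-pemphigus medication. Section 4.3 adds continuous safety review and a general condition: "Dosing and dose escalation will proceed if the DEC has determined that it would be safe and appropriate to do so".

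**The concern.** Section 8.4.1 leaves judgement at both ends: whether an event is clinically significant, and what happens after the review. What it fixes is the state in between, with dosing halted while the data are examined.

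If Cohort 1 meets the rule after its Day 42 review, that protection falls on a cohort whose last infusion was at Day 28. The bar on escalation also comes too late, because Cohort 2 may already be running. The subjects still due infusions are those on the higher dose, and nothing in the rule pauses them.

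The resulting doses do not fit together. After a Cohort 1 trigger, a new cohort may receive at most 5 mg/kg, while Cohort 2 may continue at up to 30 mg/kg pending the review.

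**Working it through.** The protocol states no figure to reproduce. The check has two parts: whether the schedule permits the sequence, and how much dosing would be exposed. No event rate is assumed.

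**Inputs**

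- Infusions at start + 0, 7, 14, 21 and 28 days (9.3).
- Eight subjects per cohort (4.3).
- Second subject at least 24 hours after the first; 7-day data on both reviewed "prior to dosing the remaining 6 subjects in the cohort" (9.2).
- Next cohort opens after review of data through Day 42 (4.3, 11.5).
- Adverse events collected to Day 112 (11.2, 7.18).
- Safety laboratory tests at Days 42, 56, 84 and 112 (6.7).

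**Window for a late trigger.** For the last Cohort 1 subject, 112 − 42 = 70 days nominal. With the visit windows (Day 42 ± 3, Day 112 ± 5) it runs from 107 − 45 = 62 to 117 − 39 = 78 days. Only the event that completes the count has to fall here; an earlier event in another subject still counts.

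**Fastest Cohort 2 calendar**, on the study-day clock of the last Cohort 1 subject:

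| Cohort 2 subject | Start | Infusion days | Due after Day 56 | After Day 63 | After Day 70 |
|---|---|---|---|---|---|
| 1 | 42 | 42, 49, 56, 63, 70 | 2 | 1 | 0 |
| 2 | 43 | 43, 50, 57, 64, 71 | 3 | 2 | 1 |
| 3–8 (six subjects) | 43 + 7 = 50 | 50, 57, 64, 71, 78 | 6 × 4 = 24 | 6 × 3 = 18 | 6 × 2 = 12 |
| **Total of 8 × 5 = 40** | | | **29** | **21** | **13** |

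Dosing spans 78 − 42 = 36 days. A trigger at Day 56 leaves 29/40 = 72.5% of infusions due, with all eight subjects already started.

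**Cohort 1 follow-up during that span.** If Cohort 1 enrolled on the same pattern, its subjects started at Days −8, −7 and 0 (six subjects). Their follow-up ends at Days 104, 105 and 112, all after Day 78. Their Day 56 ± 5 visits fall at Days 43–53, 44–54 and 51–61, all inside Days 42–78.

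**Later opening of Cohort 2.** With a delay of k days, overlap with the last Cohort 1 subject's follow-up = min(36, 70 − k) days, and not below zero.

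- k ≤ 34: the full 36 days overlap (42 + 34 + 36 = 112).
- k ≥ 70: no overlap.
- k = 28: a trigger at the scheduled Day 84 visit (56 + 28) again leaves 29 of 40 infusions due.

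**Dose contrast.** After a Cohort 1 trigger, a new cohort may receive at most 10 × 0.5 = 5 mg/kg, against up to 30 mg/kg in Cohort 2. If Cohort 2 is at 30 mg/kg and triggers late, a new cohort may receive at most 30 × 0.7 = 21 mg/kg, against up to 45 mg/kg in Cohort 3.

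**Do other rules reach these subjects?** Section 8.4.2 needs a Grade 4 event. Section 8.4.3 acts on a subject's own events or medication needs. The standing DEC duty in 14.5 during the study names drug-related serious events, and a Grade 3 event need not be serious. Section 11.3.9.2 requires 24-hour reporting only for deaths, serious events and pregnancies.

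**The case against.** The strongest reply is that the protocol uses graduated responses and leaves the rest to the DEC. A Grade 4 event suspends everyone, clustered Grade 3 events halt the affected cohort, and individual events stop the individual. A Cohort 1 trigger brings a mandatory review of all safety data. Section 4.3 makes dosing itself, as well as escalation, depend on the DEC's judgement, and the DEC can end the study at any time. All of this stands, so subjects are not without oversight. But these powers are discretionary and name no pause. The same discretion existed when the protocol fixed automatic stops in 8.4.1 and 8.4.2.

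A second reply is textual. A rule met while Cohort 2 is being dosed might be read as met during Cohort 2, in which case resumption implies that the running cohort was halted. The halt, however, is expressly confined to the cohort that met the rule. Reading the bar on escalation as closing Cohort 2 to new subjects would still leave those partway through five doses.

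A third reply concerns size and likelihood. Same-day opening at Day 42 is barely attainable, since the review must include central laboratory results, and Cohort 1 may enrol slowly in a rare disease. The 29 of 40 is therefore a fastest-calendar figure and not an expected exposure. A qualifying event two weeks or more after the last dose may also be uncommon: infusion reactions are acute, and a weak temporal relationship counts against relatedness (11.3.5). These points limit how often the gap would matter without closing it. Section 9.6.2 places IgG recovery within about four weeks of multiple dosing, from primate data. That is near Day 56, so the Day 42 review may fall while IgG is still low.

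**Conclusion.** The concern holds and should be fixed. As written, a Grade 3 trigger reached after a cohort's Day 42 review halts a cohort with no infusions left and sets no interim status for subjects already on a higher dose.

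On the fastest calendar, 29, 21 or 13 of 40 Cohort 2 infusions remain due if the trigger comes at Day 56, 63 or 70 of the last Cohort 1 subject. These counts assume immediate opening of Cohort 2, minimum spacing and simultaneous start of its last six subjects. Full overlap with that subject's follow-up persists for opening delays up to 34 days and disappears at 70. The probability of a late trigger cannot be estimated from the protocol.

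The conclusion concerns what is pre-specified; the DEC's discretionary powers remain. It rests on the latest version of section 8.4.1 in the part of the protocol at hand.

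**What to change.** Add to section 8.4.1 and to the synopsis dose-escalation rules:

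> If any cohort meets this rule, including after its Day 42 review, dosing in that cohort and in every cohort at the same or a higher dose is suspended until the DEC has reviewed all safety data and decided how to proceed.

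This extends the kind of suspension already used in 8.4.2 and leaves the later decision with the DEC.

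The cost is one sentence in two places in an amendment, with no new data, visits or subjects. The downside is a possible temporary pause of a cohort that has not itself met the rule, which may push infusions outside their ± 6 hour windows. The amendment could also state how infusions missed during a pause are handled.

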#### **8.4.2 Study Stopping Rule**

If any subject experiences a life-threatening AE (Grade 4) that is considered to be related to study drug, further dosing in all enrolled subjects will be suspended until the DEC has evaluated the event and determined the appropriate course of action. At any time during the study, the study may be discontinued if the DEC determines that further drug exposure would pose an undue risk to subjects.

#### **8.4.3 Individual Stopping Rule**

Dosing for any individual subject will be discontinued (i.e., no further study drug will be given to that subject) if the subject experiences any study drug-related SAE or any study drug-related non-SAE adverse event that, in the judgement of the Investigator (following consultation with the Medical Monitor, if desired) suggest that it could be unsafe to administer further study drug to that subject. Additionally, a subject will be discontinued from further treatment with study drug, at the discretion of the Investigator with consultation with the Medical Monitor, if they require a significant increase in dose(s) of anti-pemphigus medication(s) for the management of pemphigus.

## 9 STUDY DRUG

For detailed information regarding SYNT001 preparation and administration, refer to the Pharmacy Manual.

### 9.1 SYNT001

SYNT001 is provided in vials containing 5 mL SYNT001 (extractable volume) at a nominal concentration of 50 mg/mL. The product is supplied as a liquid at pH  $6.5 \pm 0.5$ . SYNT001 is diluted in Dextrose 5% in Water (D5W) to prepare the solution for infusion. SYNT001 will be infused via IV in 250 mL over 1 hour using a 0.2-micron, inline filter.

Two cohorts of 8 eligible subjects each will receive 5 once-weekly 60-minute infusions of SYNT001 in planned doses of 10 mg/kg or 30 mg/kg. Based on review of safety, PD, and clinical outcomes of these two cohorts, a third cohort of up to 8 subjects may be treated at another dose, with a maximum dose of 45 mg/kg, but may also be lower than 10 mg/kg or between 10 and 30 mg/kg, inclusive.

The specification for host cell DNA in SYNT001 is  $< 2$  pg/mg, the limit of quantitation of the assay. To comply with regulatory guidelines, which specify a maximum level of 10 ng host cell DNA per dose, dosing is limited to 5000 mg of SYNT001. Therefore, the maximum subject weight allowed for enrollment into the 30 mg/kg dose cohort is 166 kg and the maximum subject weight allowed for enrollment into the highest dose possible in this study (45 mg/kg) is 111 kg.

### 9.2 Cohort Dosing

Cohorts will be dosed sequentially beginning with Cohort 1. The first 2 subjects will be dosed at least 24 hours apart. A review of the 24-hour safety data for the first subject will be performed to ensure that there are no overt safety concerns before dosing the second subject. A review of the 7-day safety data for the first 2 subjects will be performed prior to dosing the remaining 6 subjects in the cohort. Cohort 2, and Cohort 3 if added, will be dosed per the same schedule

### 9.3 Timing of Dosing

On Days 0, 7, 14, 21, and 28, subjects will receive a 60-minute IV infusion of SYNT001 in the morning. The date and time the dose is administered will be recorded.

### 9.4 Identity of Investigational Products

All supplies of SYNT001 will be supplied by Syntimmune and must be stored refrigerated ( $2^{\circ}\text{C}$  to  $8^{\circ}\text{C}/36^{\circ}\text{F}$  to  $46^{\circ}\text{F}$ ) in the carton and protected from light, in a securely locked area, accessible

to authorized persons only, until needed for dose preparation. Qualified site personnel will inventory the investigational product received and will maintain records of disposition of the drug, including dates, quantity and use.

### **9.5 Investigational Product Retention at Study Site**

The Investigator (or designee) is responsible for maintaining accurate accountability records of the investigational product throughout the clinical study. All study drug received at the site must be inventoried and accounted for in an accountability log provided by the Sponsor. All dispensing and accountability records will be available for Sponsor review. Study drug accountability will be verified during on-site monitoring visits.

Upon the completion or termination of the study, and upon written authorization from the Sponsor, or its representative, all unused and/or partially used study drug should be returned or destroyed at the investigational site, as specified by Sponsor. It is the Investigator's responsibility to ensure that the Sponsor, or its representative, has provided written authorization that procedures for proper disposal of the study drug have been established, and that appropriate records of the disposal are documented and maintained. No unused study drug may be disposed until fully accounted for by the Sponsor monitor (or designee)

### **9.6 Warnings and Precautions**

**Note:** Subjects must not receive any vaccinations from within 2 weeks of screening until Day 56.

#### **9.6.1 Infusion Reaction**

SYNT001 will be given as an IV infusion over 1 hour. As with all mAbs administered by IV infusion, infusion reactions are possible. In nonclinical testing of SYNT001 in NHPs, clinical observations were limited to infusion reactions due to the immunogenicity of SYNT001 in NHPs. These reactions included transient emesis/vomitus which typically occurred within 1 hour of dosing at all dose groups, but only after the third weekly infusion following the development of ADAs. Transient histamine-type responses were noted 30 minutes post-dose in some animals in all dose groups, but only following the third weekly infusion as above. These reactions were consistent with a histamine reaction (decreased activity, periocular swelling, erythema, facial flushing, eyelids partially/completely closed, and/or generalized weakness). With the exception of vomitus/emesis and red skin discoloration associated with injection or blood draw sites, these observations spontaneously resolved within 1-hour post-dose. Subsequent pretreatment with intramuscular diphenhydramine prevented further histamine-type reactions. All doses of SYNT001 were administered by bolus infusion over approximately 5 minutes in the NHP

studies. However, all of the observed infusion reactions (including vomitus/emesis and histamine-type reactions) associated with ADAs are not at all predictive of what may occur in humans (Bugelski and Treacy, 2004; Ponce et al., 2009) and furthermore, are not considered relevant to predicting responses in humans [ICH S6(R1) 2011].

Typically, infusion reactions to monoclonal antibodies observed in human studies develop within 30 minutes to 2 hours after the initiation of drug infusion, although symptoms may be delayed for up to 24 hours. Most are mild in severity, although severe and even fatal reactions can occur.

[figure not shown]
